### 391 **9.2 Protocol Adherence and Retention**

392 The following tabulations and analyses will be performed to assess protocol adherence for the  
393 study:

- 394 • Number of protocol and procedural deviations per subject along with the number and  
395 percentage of subjects with each number of deviations
- 396 • Number of protocol and procedural deviations by severity with brief descriptions listed
- 397 • Flow chart accounting for all subjects at all visits post randomization to assess visit  
398 completion rates
- 399 • A flow chart accounting for the number of subjects enrolled, the number of dropouts pre-  
400 and post-randomization, and the number of subjects eligible to be included in the primary  
401 analysis
- 402 • Number of and reasons for unscheduled visits

## 403 **10. Baseline Descriptive Statistics**

404 Baseline demographic and clinical characteristics of the cohort of all randomized subjects will be  
405 summarized in a table. Descriptive statistics will be tabulated overall and by randomization  
406 group. For continuous variables, summary statistics appropriate to the distribution will be given.  
407 For discrete variables, number and percentage will be reported for each category. The following  
408 baseline CGM metrics will be included in the table:

- % Time in Range (3.9-10.0 mmol/L)
- Mean of sensor glucose levels
- Standard deviation of glucose levels
- Coefficient of variation of glucose levels
- % Time >10.0 and >16.7 mmol/L
- % Time <3.9, <3.5, and <3.0 mmol/L
- Area under the curve of glucose levels below 3.5 mmol/L and below 3.0mmol/L

## 11. Planned Interim Analyses

No formal interim analyses or stopping guidelines are planned for this study.

The DSMB will review data collected for the study every six months. The data to be reviewed will include information regarding all of the following:

- Status of randomized participants
- Recruitment rates by month and by site
- Baseline demographic and clinical characteristics
- Dropped participants and reasons for discontinuing
- Reportable adverse events

## 12. Subgroup Analyses

No subgroup analyses are planned for this study.

## 13. Multiple Comparisons/Multiplicity

### 13.1 Primary analysis and other key secondary outcomes

For the primary endpoint and other key endpoints listed in section 4, the familywise type I error rate (FWER) will be controlled at two-sided  $\alpha = 0.05$ . A gatekeeping strategy will be used, where the primary endpoint will be tested first, if passing the significance testing, other key endpoints will be tested in the order listed below using the fixed-sequence method at  $\alpha = 0.05$ :

- Time spent with sensor glucose levels between 3.9 to 10.0 mmol/l (70 to 180 mg/dl)
- Time spent above target glucose (10.0 mmol/l) (180 mg/dl)
- HbA1c
- Average of glucose levels
- Time spent below target glucose (3.9 mmol/l) (70 mg/dl)

Additional details are provided in section 6.3.

### 13.2 Other Secondary Analyses

For the other secondary endpoints listed in section 4, Benjamini-Hochberg false discovery rate (FDR) adjusted p-values will be calculated within each subcategory below:

#### CGM derived indices:

- Standard deviation, and coefficient of variation of glucose levels
- Time with glucose levels <3.5 mmol/L (63 mg/dL) and <3.0 mmol/l (54 mg/dl)
- Time with glucose levels in significant hyperglycemia (glucose levels > 16.7 mmol/l) (300 mg/dl)
- AUC of glucose below 3.5 mmol/l (63 mg/dl) and below 3.0 mmol/l (54 mg/dl)

448 Insulin and Other Endpoints:

- BMI standard deviation score
- Total, basal, and bolus insulin dose

451 Questionnaires:

- Strengths and Difficulties Questionnaire
  - Emotional Problems Subscale
  - Conduct Problems Subscale
  - Hyperactivity Subscale
  - Peer Problems Subscale
  - Prosocial Subscale
  - Total Difficulties Score
- Hypoglycemia Fear Survey
  - Behavior Subscale
  - Worry Subscale
- WHO-5
- Epworth Sleepiness Scale

464 Analyses by Time of Day:

- Percent time with glucose levels spent in the target range (3.9 to 10.0 mmol/L)
- Mean of glucose levels
- Standard deviation of glucose levels
- Percent time with glucose levels below 3.9 mmol/L
- Total insulin dose

470 During the extension phase, Benjamini-Hochberg false discovery rate (FDR) adjusted p-values  
471 will be calculated within these subcategories:

472 CGM derived indices and HbA1c metrics:

- Time spent above target glucose (10.0 mmol/l) (180 mg/dl)
- HbA1c at 18 months
- Average of glucose levels
- Time spent below target glucose (3.9 mmol/l) (70 mg/dl)
- Standard deviation, and coefficient of variation of glucose levels
- Time with glucose levels <3.0 mmol/l (54 mg/dl)
- Time with glucose levels in significant hyperglycemia (glucose levels > 16.7 mmol/l) (300 mg/dl)

481 Insulin and Other Endpoints:

- BMI SDS
- Total, basal, and bolus insulin dose

484 Questionnaire Scores:

- Strengths and Difficulties Questionnaire
- Hypoglycemia Fear Survey
- WHO-5
- Epworth Sleepiness Scale

489        • INSPIRE Survey  
490

491 **14. Exploratory Analyses**  
492 No exploratory analyses will be performed for this study.  
493

494 **15. Additional Analyses after Version 2.0 and Clarifications of Previous  
495 Analyses**

496 **15.1 Post-Hoc Secondary Insulin Outcomes in Units/kg/day**  
497 Secondary insulin outcomes as previously outlined in section 7.4.2 were reported and tested in  
500 Units/day. Post-hoc analysis of secondary Insulin outcomes in Units/kg/day will parallel the  
501 primary analysis. A ranked normal score transformation will be applied to all highly skewed  
502 secondary outcomes.

503 Insulin outcomes measured in U/kg/day will be treated as missing for a period if either the  
504 insulin dose or the patient's weight is missing for that period. Previous measurements will not be  
505 used to impute missing values

506 Benjamini-Hochberg false discovery rate (FDR) adjusted p-values will be calculated. Post-hoc  
507 secondary insulin outcomes in Units/kg/day will be added to the *Insulin and Other Endpoints*  
508 subcategory previously defined in section 13.2. Subcategory for FDR correction will now  
509 include the following seven (7) outcomes:

510        • Old analyses:  
511             BMI standard deviation score  
512             Total insulin (Units/day)  
513             Basal insulin (Units/day)  
514             Bolus insulin (Units/day)  
515        • New analyses:  
516             Total insulin (Units/kg/day)  
517             Basal insulin (Units/kg/day)  
518             Bolus insulin (Units/kg/day)

519 **15.2 Post-Hoc Secondary Insulin Outcomes in Units/kg/day by Time of Day**

520 Secondary total insulin outcome by time of day as previously outlined in section 7.5 was  
521 reported and tested in Units/day. Post-hoc analysis of secondary total insulin outcome in  
522 Units/kg/day will parallel the primary analysis, with the inclusion of a treatment by time of day  
523 interaction. The p-value for the interaction term will be reported. A ranked normal score  
524 transformation will be applied to all highly skewed secondary outcomes.

525 Where weight is missing at a follow-up visit, insulin outcomes in U/kg/day will be treated as  
526 missing.

527 Benjamini-Hochberg false discovery rate (FDR) adjusted p-values will be calculated. Post-hoc  
528 secondary insulin outcomes by time of day in Units/kg/day will be added to the Analyses by Time  
529 of Day subcategory previously defined in section 13.2. Subcategory for FDR correction will  
530 include the following six (6) outcomes:

531     • Old analyses:

532         ○ Percent time with glucose levels spent in the target range (3.9 to 10.0 mmol/L)  
533         ○ Mean of glucose levels  
534         ○ Standard deviation of glucose levels  
535         ○ Percent time with glucose levels below 3.9 mmol/L  
536         ○ Total insulin dose (Units/day)

537     • New analysis:

538         ○ Total insulin (Units/kg/day)

539

540 **15.3 Post-Hoc Secondary Tabulation by Time of Day**  
541 Summary statistics for the following outcome metrics will be tabulated separately for daytime  
542 (defined as 8am to less than 12am) and nighttime (defined as 12am to less than 8am) over the  
543 four month period:

544     • Basal insulin dose (Units/kg/day)  
545     • Bolus insulin dose (Units/kg/day)

546

547 **15.4 Clarification for Secondary Outcomes**

548     • Analysis of secondary HbA1c outcomes previously outlined in section 7.4.3. will parallel  
549         the primary analysis. A ranked normal score transformation will be applied to all highly  
550         skewed secondary outcomes.

551

552     • Analysis of secondary clinical outcomes previously outlined in section 7.4.4. will parallel  
553         the primary analysis. A ranked normal score transformation will be applied to all highly  
554         skewed secondary outcomes.

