## Revision History

The following table outlines changes made to the Statistical Analysis Plan.

Version Number	Author	Approver	Effective Date	Study Stage
1.0	[name]	[name]	04/04/2019	Protocol development
1.1	[name]	[name]	06/19/2019	Enrollment
1.2	[name]	[name]	07/11/2019	Enrollment
1.3	[name]	[name]	07/13/2020	Follow-up
2.0	[name]	[name]	09/01/2020	Follow-up
3.0	[name]	[name]	05/05/2021	Initial SAP analyses completed

Version Number	Revision Description
1.1	Clarified when the end of the period occurs for safety analyses and that secondary analyses by time of day include the same subjects as the primary analysis
1.2	Clarified the scoring of the INSPIRE survey
1.3	Added in the questionnaires for the sleep sub-study. Changed the definition of daytime and nighttime to be consistent with the protocol.
2.0	Added in analyses for the extension phase
3.0	Added post-hoc secondary insulin analyses in Units/kg/day. Added post-hoc secondary insulin analyses in Units/kg/day by time of day. Added in post-hoc tabulation of basal and bolus in Units/kg/day by time of day. Clarified analyses of secondary HbA1c and clinical outcomes.

23

24

[name]  
I am electronically signing this document  
2021-05-05 16:48:04:00

25 Author: \_\_\_\_\_

26

27

[name]  
I am digitally signing this document

28  
29 Senior Statistician: \_\_\_\_\_ 2021-05-05 18:51:04:00

30

31 Jaeb Principal Investigator: \_\_\_\_\_

32

33 **1. Overview**

34 This document outlines the statistical analyses to be performed for the KidsAP02 study. The  
35 approach to sample size and statistical analyses for this study are summarized below.

36 This is an open-label, multicenter, randomized, two period crossover study to assess the efficacy  
37 and safety of closed loop (CL) insulin delivery in comparison with sensor augmented/insulin  
38 pump (SAP) therapy with continuous glucose monitoring (CGM) over four months in children  
39 with type I diabetes aged 1-7 years. Approximately 72 subjects are expected to be randomized  
40 and enter the trial. All participants will receive both interventions, and the order of receiving  
41 them will be randomized based on a 1:1 ratio. Randomization will be preceded by a 2-4 week  
42 run-in period where subjects must demonstrate competency and compliance in using the study  

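### Protocol and SAP give opposite multiplicity rules for the extension secondary endpoints, and SAP 15.1 and 15.2 add post-hoc insulin tests to pre-specified FDR families

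*Combined protocol and SAP*

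**What the plan says.** **Extension.** Protocol 14.4.2 lists the extension secondary endpoints in three groups (CGM and HbA1c; insulin and other; questionnaires), calls them exploratory and says that no multiplicity correction will be made. SAP 13.2 lists the same three groups and prescribes Benjamini-Hochberg adjusted p-values within each.

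**Main study.** Protocol 14.1 says that the secondary analyses will have no formal correction. Protocol 14.3 prescribes Benjamini-Hochberg adjusted p-values within subcategories, and SAP 13.2 does the same.

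**Post-hoc additions.** SAP 13.2 defines a main-study family called "Insulin and Other Endpoints" with four tests (BMI SDS; total, basal and bolus insulin) and a time-of-day family with five. The SAP revision history records version 3.0 (05/05/2021) at the stage "Initial SAP analyses completed". In that version:

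- SAP 15.1 opens with "Secondary insulin outcomes as previously outlined in section 7.4.2 were reported and tested in" Units/day. It adds three Units/kg/day tests to the "subcategory previously defined in section 13.2. Subcategory for FDR correction will now" "include the following seven (7) outcomes".
- SAP 15.2 opens with "Secondary total insulin outcome by time of day as previously outlined in section 7.5 was" likewise already tested. It says that "secondary insulin outcomes by time of day in Units/kg/day will be added to the Analyses by Time" of Day family, which is to "include the following six (6) outcomes".

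Both sections head the additions as post hoc and list the members as old and new. Neither says whether the adjusted values from the families of four and five are kept.

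**The concern.** The extension conflict is a plain contradiction. The same outcome gets an uncorrected p-value under one document and an adjusted one under the other, and nothing says which document governs.

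The post-hoc additions raise a different problem. A Benjamini-Hochberg adjusted p-value depends on every member of its family. Once new tests join, the adjusted values of the old tests are functions of the new ones. Here the new tests were chosen after related results had been reported. The affected tests include some that are not insulin outcomes: BMI SDS in one family, and the time-of-day interactions for time in range, mean glucose, glucose SD and time below 3.9 mmol/l in the other. Pre-specified results should not depend on a later choice of what else to test.

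**Working it through.** **Family sizes.** Counting the lists in SAP 13.2, 15.1 and 15.2 gives 4 + 3 = 7 and 5 + 1 = 6, which agrees with the sizes stated in SAP 15.1 and 15.2.

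**Formula.** With m tests sorted by p-value, the adjusted value of the i-th smallest is the minimum over j ≥ i of p(j) × m / j.

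**Range of change in a pre-specified adjusted p-value.** If k tests are added to a family of m, the multiplier goes from m to m + k, and an old test of rank r moves to a rank between r and r + k. The ratio of new to old is largest when no rank moves, and smallest when the lowest-ranked test is overtaken by all k.

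| Family | Largest ratio | Smallest ratio |
|---|---|---|
| Insulin and BMI, 4 to 7 | 7/4 = 1.75 | (7/4)/4 = 0.4375 |
| Time of day, 5 to 6 | 6/5 = 1.20 | (6/2)/5 = 0.60 |

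If each Units/kg/day p-value equalled its Units/day counterpart, the insulin and BMI range would narrow to (7/2)/4 = 0.875 up to 1.75. A search over 60,000 random p-value sets per case reached these limits and never passed them.

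**Illustrations.** The documents give no p-values, so all of these are assumed.

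- Insulin and BMI, pre-specified p-values 0.012, 0.20, 0.30, 0.50. The smallest adjusts to 0.012 × 4 = 0.048.
  - Rise: BMI SDS is the 0.012 and the three insulin values are duplicated. The result is 0.012 × 7 = 0.084.
  - Fall: an insulin test is the 0.012 and is duplicated. The result is 0.012 × 7/2 = 0.042, whether BMI SDS is the 0.50 or the 0.20.
- No change: insulin 0.03, 0.035, 0.04 (duplicated) and BMI SDS 0.045 give 0.045 for every test at both family sizes.
- Time of day, p-values 0.009, 0.20, 0.30, 0.40, 0.50. The smallest adjusts to 0.009 × 5 = 0.045. Adding 0.50 gives 0.009 × 6 = 0.054; adding 0.009 gives 0.009 × 6/2 = 0.027.

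**The new tests themselves.** Merging can tighten or loosen the correction of the three Units/kg/day insulin tests.

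- Tighter: at an assumed level of 0.05, a lone smallest p-value must reach 0.05/7 = 0.0071 in the merged family, against 0.05/3 = 0.0167 in a family of three.
- Looser: post-hoc p-values 0.035, 0.30, 0.50 give 0.035 × 3 = 0.105 for the smallest in a family of three. Merged with pre-specified values 0.001, 0.002, 0.003, 0.004, it has rank 5 and becomes 0.035 × 7/5 = 0.049.

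**Extension.** The CGM and HbA1c group in SAP 13.2 has eight tests: time above 10.0, HbA1c, mean glucose, time below 3.9, SD, coefficient of variation, time below 3.0 and time above 16.7 mmol/l. At an assumed level of 0.05, a lone smallest p-value must reach 0.05/8 = 0.00625 under SAP 13.2, against 0.05 under protocol 14.4.2.

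**The case against.** The strongest reply is that version 3.0 is open about what it does. The additions are headed post hoc, the change is dated with its study stage, and SAP 15.1 and 15.2 state the new family sizes and list every member. A reader might infer that the family behind an adjusted value cannot be identified; the text does not support that. The natural reading is that the enlarged families replace the old ones. What stands is that replacement makes pre-specified values depend on later tests, and that the SAP does not say whether the original values will also be shown.

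A reader might also infer that the families were enlarged to move a result. Nothing in the documents shows this. They give no observed p-values, and the change can go in either direction. Nor is it stated that every old test had been run: SAP 15.1 and 15.2 say so for the Units/day insulin tests, while for BMI SDS and the glucose interactions it is inferred from the stage label.

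Because SAP 13.2 uses the insulin family name for both phases, one could ask whether the extension family is enlarged too. The statement that the outcomes had already been reported and tested, in a document of May 2021, points to the main study: protocol section 23 expects the last extension participant to finish in October 2022.

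It is also fair that little hangs on these tests. Protocol 14.3 and 14.4.2 call the endpoints exploratory, SAP 7.5 expects low power by time of day, and no FDR cut-off is stated, so no pass or fail decision is defined. That limits the importance but does not remove the contradiction between the documents.

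**Conclusion.** Both parts hold, with low stakes. The extension conflict between protocol 14.4.2 and SAP 13.2 is the clearer defect, and protocol 14.1 against 14.3 is the same kind of inconsistency. The enlarged families make pre-specified adjusted p-values depend on later tests. The possible change is a factor of 0.4375 to 1.75 for insulin and BMI, and 0.60 to 1.20 for time of day. These are limits over all possible p-values, not estimates, and values may also stay the same.

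The conclusion rests on reading SAP 15.1 and 15.2 as replacing the original adjusted values. The comparisons with 0.05 use an assumed level. The primary endpoint and the four key endpoints are tested in a fixed sequence and are not affected.

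**What to change.** 1. Before the extension analysis, state one correction rule in both documents. The simplest is the FDR rule already in SAP 13.2, with protocol 14.4.2 changed to match. Limit the sentence in protocol 14.1 so that it agrees with 14.3.
2. In SAP 15.1 and 15.2, state that the pre-specified tests are reported with adjusted p-values from the original SAP 13.2 families of four and five.
3. Report the Units/kg/day tests in a separate block labelled post hoc, and name the family used for their adjustment. Do not describe the merged family as always the stricter one.

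The cost is a few sentences in the SAP, two recalculated sets of adjusted p-values, and protocol wording that may need an amendment. The drawback is that two sets of adjusted values must be explained in the report.
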